### **7.3.3. Device Malfunctions and Failures**

All reported device observations / performance issues, malfunctions or failures of the Merit WRAPSODY Endovascular Stent Graft System are required to be documented in the eCRF. In the event of a suspected observation or device problem, the investigational device shall be returned to the Sponsor for analysis. Potential device failures and malfunctions should also be documented in the subject's medical record. Instructions for returning the investigational device are included in the Manual of Operations Binder.

NOTE: Device failures or malfunctions are NOT to be reported as adverse events. However, if there is an adverse event that results from a device failure or malfunction, that specific event would be recorded in the usual manner on the AE eCRF.

## **8.0 RISK / BENEFIT ASSESSMENT**

### **8.1 Risks to the Subject**

#### **8.1.1. Risk Analysis**

The WRAPSODY Endovascular Stent Graft System or the WAVE Study treatment procedure may result in failures or complications similar to other peripheral stents/stent grafts with similar indications for use. Prior human use and preclinical studies of the WRAPSODY Stent Graft System have not shown any additional risks. Documented risks of peripheral stents/stent grafts and/or the endovascular treatment procedure include, but are not limited to (potential risks are listed in alphabetical order and not per risk level):

- Access-site complications
- Allergic reaction to contrast media / medications
- Aneurysm
- Arteriovenous (AV) fistula
- Bleeding complications
- Cardiac arrest
- Cardiac arrhythmia
- Death
- Device embolization
- Device malfunction
- Device migration
- Device occlusion / thrombosis
- Embolism and/or vessel thrombosis
- Emergency or non-emergency access circuit intervention
- Extravasation of contrast media
- Fracture of the guide wire or any component of the device that may or may not lead to device embolism, serious injury or surgical intervention

- Hematoma
- Infection or fever
- Ischemia
- Myocardial infarction or coronary ischemia
- Neurological deficit
- Placement of a bailout stent / stent graft
- Pseudoaneurysm
- Radiation exposure
- Reaction to contrast media / medication
- Respiratory distress or failure
- Restenosis of the treated segment
- Serious injury requiring surgical intervention
- Seroma
- Stent graft compression
- Stent graft kinking
- Stent strut fracture(s)
- Stroke or TIA
- Transfusion
- Total occlusion of the vascular access circuit
- Vascular complications that may require surgical repair (conversion to open surgery)
- Vessel dissection
- Vessel perforation
- Vessel rupture
- Vessel spasm

These risks are present in any endovascular treatment procedure for which the study subjects would be indicated because of their disease, and the subject's physician will review these risks with the subject. Standard of care practice should be followed for preparing a subject for endovascular intervention, including medication and vascular access.

#### 8.1.2. Risk Minimalization

As with any endovascular procedure, appropriate safety precautions will be followed. In addition, this protocol provides additional steps to minimize risk to study subjects. These include the following:

- **Investigator Selection:** The Investigators in this study are selected based on their experience in treating subjects with vascular access circuit dysfunction and performing endovascular treatment procedures, including stent/ stent graft placement and peripheral balloon angioplasty and the availability of appropriate resources and facilities to conduct the study.
- **Investigator Training:** Investigators will be trained in proper device operation prior to study start. Training will include didactic and hands-on training with the WRAPSODY Stent Graft System (e.g., bench-top model, animal lab training).
  - Enhanced training shall be conducted with all clinical investigators on WRAPSODY Stent Graft sizing and placement. Each investigator shall deploy a demo device prior to enrollment.
- **Subject Screening:** This protocol includes appropriate precautions in subject selection. For example, subjects with significant co-morbidities or uncontrolled cardiovascular or other disease will be excluded.

Patients who do not meet all inclusion criteria and none of the exclusion criteria, including known allergy to nickel alloy, will be excluded from this protocol per IFU Contraindications for Use.

## **8.2 Potential Benefits**

Prior human clinical experience in a population of 46 subjects has validated that the WRAPSODY Stent Graft System can be used to safely and effectively treat stenoses and occlusions within the venous outflow circuit and graft/vein anastomosis, resulting in acute and long-term luminal patency. The WAVE Study is intended to evaluate the safety and effectiveness of the WRAPSODY Stent Graft System in a larger clinical population.

## **9.0 STATISTICAL ANALYSIS PLAN**

This study comprises two cohorts:

1. Subjects with AVF access who have stenosis or occlusion in a peripheral vein, including the cephalic arch will undergo 1:1 randomization to the Merit WRAPSODY Stent Graft or PTA (AVF Peripheral cohort);
2. Subjects with AVG access who have stenosis or occlusion at the anastomosis or juxta-anastomosis will be treated with the Merit WRAPSODY Stent Graft (AVG Anastomosis cohort).

Each cohort will be analyzed separately.

### **9.1 Analysis Population**

Intent to Treat Population: The Intent to Treat (ITT) population will include all randomized subjects in the AVF Peripheral cohort, and all subjects enrolled in the AVG Anastomosis cohort.

Modified Intent to Treat Population: The Modified Intent to Treat (mITT) population will include all ITT subjects who receive treatment.

Per Protocol Population: The Per Protocol (PP) population will include all mITT subjects who additionally met all inclusion/exclusion criteria. This is a secondary analysis set for the primary safety and effectiveness endpoints, as well as secondary endpoints.

While mITT is intended as the primary analysis set for all safety and effectiveness endpoints, the primary safety and effectiveness endpoints will additionally be evaluated in the ITT and PP analysis sets as supportive information. All subjects excluded from mITT and PP analysis sets will be described in the final study report and the reasons detailed. If the ITT and mITT analysis sets contain the same subjects, then all mITT analyses will revert to the ITT analysis set and the mITT analysis set will be eliminated.

### **9.2 General Methodology**

Subject data listings and tabular and graphical presentations of results will be provided. Descriptive statistics of continuous variables will be presented by treatment arm and include sample size, mean, median, standard deviation, minimum and maximum. For categorical variables, the number and percentage of subjects in each category will be presented by treatment arm. In general, number of subjects with missing data can be identified from the difference between number of mITT subjects and number of observations. Dichotomous variables will be evaluated using Fisher's exact tests. Categorical variables will be evaluated by Cochran-Mantel-Haenszel (CMH) Modified Ridit Scores, i.e., CMH of general association for nominal variables and CMH of row mean score for ordinal variables. Continuous variables will be evaluated by two-sample t-test. Time to event analysis will be carried out using the Kaplan-Meier method along with Greenwood standard error. If a subject does not have an event, the time point when a subject becomes un-evaluable will be considered as the censoring time for this subject. Unless otherwise specified, a two-sided 0.05 level of significance will be used to declare treatment arms significantly different.

### 9.3 Primary Endpoint Analysis

Endpoints will be analyzed using the modified intention-to-treat analysis set as described below. Each sub-study will be considered successful if both primary safety and effectiveness endpoints have been met. An additional supportive analysis may be conducted in the ITT analysis set for the primary safety and effectiveness endpoints.

#### 9.3.1. Primary Safety Endpoint

The primary safety endpoint is the proportion of subjects without any localized or systemic safety event through 30 days post study procedure that affects the access or venous outflow circuit and resulted in reintervention, hospitalization, or death (not including stenosis or thrombosis). Endovascular procedures performed to treat safety events after the index study procedure will be considered surgeries.

#### 9.3.2. Primary Effectiveness Endpoint

The primary effectiveness endpoint is the proportion of subjects with target lesion primary patency (TLPP) at 6 months (180 days). The key secondary effectiveness endpoint is the proportion of subjects with TLPP at 12 months (360 days). Calculation of these endpoints will be based on the number of subjects with adequate follow-up. In addition, these endpoints will be estimated using Kaplan Meier estimates with standard error calculated using the Greenwood method. Time to loss of TLPP is defined as the interval of uninterrupted patency from initial study procedure to the next intervention performed on the target lesion.

### 9.5 Other Safety Data

All adverse events (AEs) collected will be coded. Events will be summarized cumulatively through the following time points: 30 days, 6 months, 12 months (all AEs) and 24 months (SAEs only). Frequency count of AEs and unique number of patients who had the AEs, for each coded term, will be presented. Also, the frequency and percentage of patients who had a Serious AE (SAE), or a related AE (by relationship to both implant procedure and device) will be tabulated separately by a coded term.

### 9.6 Site Poolability

Poolability of data across clinical study sites is justified on a clinical basis (i.e., all study sites use the same protocol) the sponsor monitors the site for protocol compliance, and the data gathering instruments are identical. The Food and Drug Administration also requires a statistical assessment of site poolability.

For the two randomized cohorts, poolability of subjects across clinical sites for the primary effectiveness and safety endpoint analysis will be tested using Cox proportional hazards regression. Included as independent variables in the Cox models will be treatment, site and the treatment-by-site interaction effect; if the interaction effect is not statistically significant (defined as  $p > 0.15$  on the interaction test) or the interaction effect is significant but not qualitative in nature, all data irrespective of site will be collected in a single analysis cohort. Sites with fewer than 9 subjects will be ranked by enrollment from

low to high, then starting from the lowest enrollment site, sites will be combined into a pseudo site until the combined size reaches the median enrollment among all sites. This process will be repeated until all resulting sites have enrollment equal to or greater than 9 subjects. This analysis will be performed on the primary analysis sets including all randomized subjects. Similar analyses will be conducted to assess treatment-by-geography (US vs. OUS) interaction.

For the non-randomized cohort, poolability analysis will be performed on the primary endpoints comparing across sites and geographies after adjusting for covariates difference. Logistic regression model will be utilized to include site as an independent variable, and the study outcome as dependent variable to assess outcome difference. If the p-value of site effect is less than 0.15, further analyses will be undertaken to investigate the imbalance of the study outcome. Sites with fewer than 6 subjects will be combined into a pseudo site as above.

These analyses will be performed on the primary analysis sets.

### 9.7 Sample Size

There are two hypotheses for each of the two cohorts in the study. One is for the primary effectiveness endpoint – target lesion primary patency at 6 months, and one is for the primary safety endpoint – localized or systemic safety event through 30 days post-procedure. The AVF Peripheral cohort will be a randomized controlled sub-study (1:1) of SG vs. PTA. The AVG Anastomosis cohort is a single arm Performance Goal (PG) sub-study.

#### AVF Peripheral cohort

For the primary effectiveness endpoint, the SG treatment ( $p_T$ ) and PTA control ( $p_C$ ) groups will be compared in a superiority format under the following hypothesis.

$$H_0: p_T = p_C$$

$$H_A: p_T > p_C$$

For the primary safety endpoint, the treatment ( $\pi_T$ ) and control ( $\pi_C$ ) groups will be compared in a non-inferiority format under the following hypothesis.

$$H_0: \pi_T \geq \pi_C + 0.15$$

$$H_A: \pi_T < \pi_C + 0.15$$

Sample size for the primary effectiveness endpoint was estimated using the two-group chi-square test. Assumptions included a two-sided 0.05 alpha and at least 80% desired power to show superiority of SG to PTA. A 78% primary patency rate was assumed in treatment and 60% in control. From these assumptions a sample size of 103 per arm was calculated and with an assumed compliance of 85% yielded 122 per arm or 244 in total.

For the one-sided 0.05 test of non-inferiority of SG to PTA on the primary safety endpoint, the event-free safety composite rate was assumed to be 95% in the treatment and control groups with a non-inferiority margin of 15% using the Ferrington-Manning test. Power for non-inferiority of the primary safety endpoint was 80% and the calculated sample size was 40 per arm. After assuming 5% lost to follow-up at 30 days the number per arm was 43 or 86 in total. Therefore, the overall sample size for this study cohort was determined by the effectiveness endpoint. With a total sample size of 244 the safety endpoint will have 99% power.

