## 9.10 Analysis

For the randomized AVF Peripheral cohort, the count and percentage of subjects with TLPP at 6 months will be presented by treatment arm. The percentages will be computed as

$\hat{p}_i = 1 - \frac{n_i}{m_i}, i = T(\text{treatment}), C(\text{control})$ .  $n_i$  is the number of subjects in each treatment arm who experienced non-patency event within 180 days post procedure,  $m_i$  is the number of subjects in each

treatment arm who experienced non-patency event within 180 days or had no non-patency event but followed up for at least 150 days. The hypothesis will be tested using the chi-square test, and the differences between treatments together with a two-sided 95% confidence interval will be calculated. For the primary safety endpoint, the count and percentage of subjects with a safety event at 30 days will be presented by treatment arm. The percentages will be computed as  $\hat{p}_i = 1 - \frac{n_i}{m_i}$ ,  $i = T, C$ .  $n_i$  is the number of subjects in each treatment arm who experienced an event within 30 days post procedure,  $m_i$  is the number of subjects in each treatment arm who experienced an event within 30 days or had no event but followed up for at least 23 days. Non-inferiority on the safety endpoint will be tested using the Farrington-Manning test. The differences between treatments together with the one-sided 95% upper confidence limit will be calculated.

For the nonrandomized AVG Anastomosis cohort, a one-sided p-value will be derived based on an exact binomial test. The study device will be considered to have achieved the primary effectiveness objective if the one-sided p-value is less than 0.05. Or equivalently, the lower limit of the one-sided 95% confidence limit based on exact method is greater than 60%. The same testing methodology will be used for the primary safety endpoint in comparison to the PG of 89%.

To control the overall Type I error (two-sided  $P=0.05$  superiority and one-sided  $P=0.05$  non-inferiority) in the randomized cohorts the following fixed sequence testing procedure will be taken:

Primary effectiveness superiority; if significant at two-sided  $\alpha=0.05$ , proceed to

Primary safety non-inferiority; if significant at one-sided  $\alpha=0.05$  proceed to secondary endpoints.

The key secondary effectiveness endpoint with hypothesis testing is TLPP at 12 months (360 days). Other secondary effectiveness endpoints for hierarchical testing, in order, are:

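### AVF safety non-inferiority test: π is undefined, and the hypotheses and upper limit are on a different scale from the endpoint and its estimator

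*Combined protocol and SAP*

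**What the plan says.** The statements that govern the AVF safety test fall into two groups.

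**Event-free scale (higher is safer).**
- Section 9.3.1: "The primary safety endpoint is the proportion of subjects without any localized or systemic safety event through 30 days post study procedure". Section 4.1.1 defines the endpoint in the same way.
- Section 9.7, AVF Peripheral cohort, planning assumption: "the event-free safety composite rate was assumed to be 95% in the treatment and control groups with a non-inferiority margin of 15" per cent.
- Section 9.10: the safety percentage is 1 − n/m, where n counts subjects who had an event within 30 days.

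**Event scale (lower is safer).**
- Section 9.7, null: "H_0: \pi_T \geq \pi_C + 0.15"; alternative: "H_A: \pi_T < \pi_C + 0.15".
- Section 9.10, in the sentence before the formula, announces the percentage of subjects who had a safety event.
- Section 9.10, after the test is named: "The differences between treatments together with the one-sided 95% upper confidence limit will be calculated".
- The opening of Section 9.7 labels the safety hypothesis by the event, not by its absence. Section 9.8 describes endpoint rates in general as subjects with the endpoint over evaluable subjects, that is, n/m.

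No section defines π. Section 9.10 does not say which arm is subtracted from which, and gives no numerical criterion for the confidence limit. For the AVG cohort, Section 9.7 tests the same endpoint on the event-free scale, with a rate above 89% as the alternative.

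**The concern.** A null of the form π_T ≥ π_C + margin, rejected when an upper limit for π_T − π_C falls below the margin, is a non-inferiority test only if a larger π is worse. The only formula given for this endpoint yields a quantity for which larger is better. Put together literally, the test asks whether the stent graft is less than 15 points safer than PTA. It does not ask whether it is less than 15 points less safe.

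The test matters. Section 9.3 makes success in each sub-study depend on both primary endpoints, and the fixed sequence in Section 9.10 opens the secondary endpoints only after safety non-inferiority is shown. A programmer following the literal text would have a safety test with almost no ability to detect harm, and the planning figures would not reveal the problem.

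**Working it through.** **Inputs from Section 9.7.** 95% event-free in both arms; margin 0.15; one-sided α = 0.05; 80% power; 40 per arm, raised to 43 for 5% loss; 99% power at 244 in total. The test is Farrington-Manning. **Assumption:** 116 evaluable per arm, from 122 × 0.95 = 115.9.

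**1. Reproduce the plan's sample size.** With restricted maximum-likelihood rates under the null,

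n = (z₀.₉₅·s₀ + z₀.₈₀·s₁)² / 0.15²

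- Event-free scale, null difference −0.15: restricted rates are 0.8229 and 0.9729, so s₀ = √(0.8229×0.1771 + 0.9729×0.0271) = 0.4148. Also s₁ = √(2×0.95×0.05) = 0.3082.
- n = (1.645×0.4148 + 0.8416×0.3082)² / 0.0225 = 39.4, so 40 per arm.
- Event scale, 5% in both arms, null difference +0.15: restricted rates are the complements, 0.1771 and 0.0271, so s₀ and s₁ are the same and n is again 39.4, so 40.
- 40/0.95 = 42.1, so 43 per arm and 86 in total.
- Power at 116 per arm: Φ[(0.15·√116 − 1.645×0.4148)/0.3082] = 0.9988. At 122 per arm it is 0.9992. Both agree with the stated 99%.

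The plan's figures reproduce on both scales, so they cannot show which one was meant.

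**2. Put the event-free quantity into the written null.** With π_C = 0.95, the null requires π_T ≥ 0.95 + 0.15 = 1.10, which is impossible. The alternative is true whatever the device does.

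**3. Probability of declaring non-inferiority.** Full binomial enumeration of the Farrington-Manning score test, 116 per arm, PTA 95% event-free, difference taken as stent graft minus PTA:

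| Stent graft event-free | Written hypotheses with 1 − n/m | One consistent scale |
|---|---|---|
| 95% | 0.999 | 0.999 |
| 85% | >0.9999 | 0.336 |
| 80% (at the margin) | >0.9999 | 0.049 |
| 70% | >0.9999 | 0.0001 |
| 60% | >0.9999 | <0.0001 |

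The last column can be reached in two ways: reverse the hypotheses on the event-free scale, or keep the written hypotheses and use event rates. Enumerating the written hypotheses with event rates of 5%, 20% and 30% against 5% gives 0.999, 0.049 and 0.0001, matching the 95%, 80% and 70% rows.

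**4. The confidence limit.** Take observed event-free rates of 70% and 95%. The Wald standard error (used here for simplicity) is √[(0.70×0.30 + 0.95×0.05)/116] = 0.0471, and 1.645×0.0471 = 0.0775. For stent graft minus PTA, the upper limit is −0.25 + 0.0775 = −0.172, which is below +0.15 and so passes. The lower limit is −0.25 − 0.0775 = −0.328, which is below −0.15 and so fails. Only the lower limit registers the 25-point deficit.

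**The case against.** The strongest reply is that π means the event rate. Section 9.7 uses a separate symbol, p, for patency and introduces the safety hypothesis by naming the event. Section 9.8 describes rates as n/m, and Section 9.10 announces the percentage with an event and asks for an upper limit. A 95% event-free assumption is simply the complement of 5% events, and an endpoint defined as freedom from events can be tested through its complement. On this reading the inequalities are a standard, correctly directed test, and the outlier is 1 − n/m. The same formula is used, correctly, for patency earlier in that paragraph, so it may have been carried over. An upper limit on PTA minus stent graft of event-free rates would also be valid, and the direction of the difference is not stated.

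Most of this stands. It means the hypotheses cannot be called wrong in themselves. It does not make the section consistent: under the event reading, the only formula for the safety percentage gives the complement of what its own sentence announces and of what the hypotheses need. Under the event-free reading, the hypotheses point the wrong way.

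Two stronger inferences should be resisted. A reader might conclude that the plan commits the sponsor to a test that passes an unsafe device. That needs π to be event-free, 1 − n/m to estimate π, the difference to be stent graft minus PTA, and a null of 110% to go unnoticed; the documents fix none of the first three. Naming the test as non-inferiority, with a 15-point margin, points to a proper test being intended. A reader might also take the 40 per arm as evidence that the inequalities are reversed. It is not, because the calculation is symmetric when the two rates are equal.

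**Conclusion.** The concern holds as an error of specification in a co-primary, gating test. With π undefined, the plan states the endpoint, planning rate and estimator on one scale and the hypotheses and upper limit on the other, so at least one stated element is wrong on any reading. The consequence depends on how the text is implemented. Joined literally with a stent-graft-minus-PTA difference, the test passes with probability 0.999 at equal safety and above 0.9999 when the stent graft is 10 to 35 points worse. Implemented on one scale, it passes 0.049 of the time at the 15-point margin and 0.336 at 10 points worse.

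These probabilities assume 116 evaluable per arm and a PTA event-free rate of 95%. The literal test was not shown to be incapable of failing; it passes at least 99.9% of the time in the scenarios examined. The sample size and stated power are sound on either scale. The text should be corrected before the AVF data are locked for the primary analysis.

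**What to change.** Define π in Section 9.7, state the difference as π_T − π_C (stent graft minus PTA), and use one scale throughout Sections 9.7 and 9.10. Either version will do:

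- **(a) Event rate.** Define π as the 30-day safety event rate. Keep the hypotheses and the upper limit. Replace 1 − n/m with n/m for safety. Declare non-inferiority if the one-sided 95% upper Farrington-Manning limit for π_T − π_C is below +0.15. State that 95% event-free corresponds to a 5% event rate.
- **(b) Event-free proportion.** Define π as the proportion without an event. State H₀: π_T ≤ π_C − 0.15 against H_A: π_T > π_C − 0.15. Keep 1 − n/m, and change the sentence before it so that it refers to subjects without an event. Declare non-inferiority if the one-sided 95% lower Farrington-Manning limit for π_T − π_C is above −0.15.

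Version (a) leaves the hypotheses untouched; version (b) matches the endpoint definition and the AVG cohort's safety hypothesis. The two give the same decision. The cost is wording in two sections and a check that the analysis program agrees. The 40 per arm (43 after loss), the 244 in total, the 99% power and the conduct of the trial are unaffected.
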